Subjects who discontinue treatment prematurely, regardless of the reason, should be instructed to return for an Early Termination (ET) visit within 7 days of the last administration of study treatment (Table 7 and Table 8) and before initiation of any new treatments to complete all of the ET assessments. If a subject discontinues due to pregnancy, they are not required to complete the endoscopy. If the ET visit is within 4 weeks of the last sigmoidoscopy and biopsy, these procedures do not need to be repeated.

If the ET visit is ≥ 2 weeks of the last administration of study treatment, the 2-Week Follow-Up visit is not required; however, the 4-Week Follow-Up visit should be scheduled and completed. If the ET visit is ≥ 4 weeks of the last administration of study treatment, the 4-Week Follow-Up visit is not required unless the absolute lymphocyte count (ALC) is not within normal limits.

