9.6. Virtual/Hybrid Visits

Study visits after Day 1 may be conducted via onsite (in person at the study site or specialty lab), offsite (home health visit by study staff or designee), virtual (eg, telephone, video conference), or hybrid (a combination of aforementioned visit types) depending on the nature of the study assessment, technological capability, and acceptability with institutional practices and in alignment with local law and regulatory requirements. These may take place on different days within the study visit window.

Certain assessments and/or procedures will **not** be performed in the home setting (eg, endoscopies, OCT, PFT, cardiac monitoring following treatment initiation or re-initiation, and 12-lead ECG).

Pregnancy testing and central laboratory assessments (eg, blood, stool, and urine samples) can be performed by either onsite visit or offsite visit.

Assessments or procedures that may be conducted virtually, if allowed by local law and regulation, include for example: informed consent process including obtaining written informed consent, medical and medication history to assess eligibility criteria, review of demographic information, social history, AE query, review of concomitant medications, eDiary training, and compliance review/monitoring including study drug administration and questionnaires.

During a virtual assessment, a subject may report an AE that requires a follow-up symptom-focused physical exam or diagnostic test, as determined by the Investigator. In this scenario, the Investigator may have the subject return to the study site for an unscheduled study visit to perform the assessment.

For study drug accountability, the medication bottle and remaining tablets may be visually inspected and counted on video conferencing. Subjects must return the dispensed bottle with the remaining tablets along with any empty bottles to the study site at the next onsite visit. See Section 8 for study treatment management.

Regardless of how a study visit and its associated procedures are conducted, all study procedures should be performed by qualified study site staff or qualified individual as delegated by the Principal Investigator.

Study visits are designated accordingly in the Schedules of Assessments (Table 7 and Table 8).

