2.5. Estimands

The primary and key secondary efficacy estimands to support regulatory decisions are described in Table 1. The analyses will be performed on the Full Analysis Set (FAS) as defined in Section 5.3. Other secondary efficacy variables (specified in Section 16.3.1) will have the population, intercurrent event handling strategy and population-level summary measure similar to the primary estimand. Supplementary analyses for the primary and the key secondary estimands will be performed on the modified Full Analysis Set (mFAS) and the Per Protocol populations, respectively (ICH 2019). Intercurrent events include: 1) initiate a rescue medication for UC, 2) have an increase in dose over Baseline levels in their existing UC medication, or 3) have a rescue non-drug treatment (eg, colectomy, ileostomy, or sigmoidectomy) before the

efficacy assessment. Refer to [APPENDIX 7](#) for the definition of rescue therapies (medication and medical procedures).

Table 1: List of Primary and Key Secondary Estimands

Estimand	Definition	Attribute			
		Population	Variable/Endpoint	Intercurrent Event Handling Strategy	Population-Level Summary Measure
Primary Estimand 1	Efficacy of etrasimod on clinical remission at Week 12	Randomized subjects who receive at least 1 dose of study treatment and with Baseline MMS 5 to 9	The proportion of subjects with SF = 0 (or = 1 with a ≥ 1 -point decrease from Baseline), RB = 0, and ES ≤ 1 (excluding friability) at Week 12	Subjects with any of the 3 intercurrent events ^a before the efficacy assessment will be treated as nonresponders.	Difference between etrasimod and placebo in the endpoint at Week 12
Primary Estimand 2	Efficacy of etrasimod on clinical remission at Week 52	Randomized subjects who receive at least 1 dose of study treatment and with Baseline MMS 5 to 9	The proportion of subjects with SF = 0 (or = 1 with a ≥ 1 -point decrease from Baseline), RB = 0, and ES ≤ 1 (excluding friability) at Week 52	Subjects with any of the 3 intercurrent events ^a before the efficacy assessment will be treated as nonresponders.	Difference between etrasimod and placebo in the endpoint at Week 52

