Key Secondary Estimand 6	Efficacy of etrasimod on sustained clinical remission	Randomized subjects who receive at least 1 dose of study treatment and with Baseline MMS 5 to 9	The proportion of subjects with sustained clinical remission (clinical remission at both Weeks 12 and 52)	Same as the intercurrent event handling strategy for the primary estimand	Difference between etrasimod and placebo in proportion of responders
Key Secondary Estimand 7	Efficacy of etrasimod on mucosal healing at Week 12	Randomized subjects who receive at least 1 dose of study treatment and with Baseline MMS 5 to 9	The proportion of subjects with ES of ≤ 1 (excluding friability) with histologic remission measured by a Geboes Index score < 2.0 at Week 12	Same as the intercurrent event handling strategy for the primary estimand	Difference between etrasimod and placebo in proportion of responders at Week 12
Key Secondary Estimand 8	Efficacy of etrasimod on mucosal healing at Week 52	Randomized subjects who receive at least 1 dose of study treatment and with Baseline MMS 5 to 9	The proportion of subjects with ES of ≤ 1 (excluding friability) with histologic remission measured by a Geboes Index score < 2.0 at Week 52	Same as the intercurrent event handling strategy for the primary estimand	Difference between etrasimod and placebo in proportion of responders at Week 52

^a Intercurrent events include: 1) initiate a rescue medication for UC, 2) have an increase in dose over Baseline levels in their existing UC medication, or 3) have a rescue non-drug treatment (eg, colectomy, ileostomy, or sigmoidectomy) before the efficacy assessment. Refer to [Appendix 7](#) for the definition of rescue therapies (medication and medical procedures). ES, endoscopic score; RB, rectal bleeding; SF, stool frequency; UC, ulcerative colitis.

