^d Due to overlapping windows in the RB/SF components at Week 52 and Week 48, a hierarchical algorithm will be used for the mapping. Week 52 will always be mapped first, then assess records for the Week 48 mapping. If a scheduled Week 48 and 52 visits are both present in the same visit window, they will be mapped to separate visits (ie, Week 48 and Week 52).

^e Assessments impacted by the COVID 19 pandemic are reported in the Date of Visit eCRF.

COVID-19, coronavirus disease 2019; ECG, electrocardiogram; eCRF, electronic case report form; MMS, modified Mayo Score; OCT, optical coherence tomography; PFT, pulmonary function test; RB, rectal bleeding; SF, stool frequency.

For cardiac remonitoring upon treatment reinitiation after Day 2, as manifested by more than 1 timed measurement in vital signs or electrocardiogram (ECG) parameters on the same collection date of an unscheduled visit, measurements will be mapped to analysis visit of Cardiac Remonitoring 1, Cardiac Remonitoring 2, etc. in the respective analysis dataset. For analysis, each timed measurement will be programmatically assigned to the nearest hourly timepoint (eg, Predose, 1-hour Postdose) based on their relationship to the dosing time on the same day. If the dosing date/time on the same day is missing, the timepoint will remain missing. Once mapped, these timed measurements from cardiac remonitoring visits will not be considered for any other analysis visit.

Windowing will be applied prior to any missing data calculations. The last nonmissing measurement taken prior to Day 1 (including unscheduled assessments) will be labeled as “Baseline”. Unless stated otherwise, data from all visits including scheduled, unscheduled, and ET visits will be eligible for allocation to an analysis visit. The 2-Week and 4-Week Follow-Up visits will not be included in the visit windows and will be summarized separately without any window applied.

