16.1.2. Missing Data Methods for Primary Efficacy Variables

Subjects who 1) discontinue the study for worsening of disease, lack of efficacy, or adverse event related to UC, 2) initiate a rescue medication for UC, 3) have an increase in dose over Baseline levels in their existing UC medication, or 4) have rescue medical procedure (eg, colectomy, ileostomy, or sigmoidectomy) during the study as confirmed after blinded review by clinical and medical team members before study unblinding will be considered to have a known (ie, nonmissing) outcome of nonresponse in the analysis of all efficacy endpoints at any subsequent timepoints, including the primary endpoint. The rescue medications will be identified by the Arena clinical team during blinded data review. Refer to [Appendix 7](#) for the definition of rescue therapies (medication and medical procedures). In scenarios 2 and 3 above, if a subject has an efficacy measurement collected after the initiation or dose increase from Baseline of UC medication, the observed data will be censored at the time of initiation or dose increase and they will be considered as having a nonresponse. Subjects in all 4 scenarios above may still be included in the respective Per Protocol Set, provided they do not violate other criteria for Per

Protocol Set. For example, they will be excluded from the respective Per Protocol Set if they initiate a prohibited medication before the Week 12 or Week 52 efficacy assessment that can affect efficacy of the study treatment and the indication is unrelated to UC.

Analysis visits will be mapped as per Section 6.4 before any missing data imputation method is applied.

Subjects with a missing efficacy outcome will be included in the primary analyses using the following missing data methods:

- Primary method: Single imputation as nonresponder
- Sensitivity analyses: Multiple imputation under missing at random (MAR), tipping point analysis, multiple imputation with Copy Reference (CR) under missing not at random (MNAR), and a hybrid imputation with multiple imputation to handle missing endoscopy data due to the COVID-19 pandemic impact and nonresponder imputation (NRI) for missing data not due to the COVID-19 pandemic impact. More details are provided in Section 16.1.4
- Supplementary analyses: mFAS analysis with data as observed, Per Protocol Set analysis (Week 12 Per Protocol Set for Week 12 endpoints and Week 52 Per Protocol Set for Week 52 endpoints)

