APPENDIX 7: CLASSIFICATION OF RESCUE THERAPY

This appendix outlines the algorithm for the Arena clinical team/medical reviewers to classify rescue therapies for ulcerative colitis (UC) in a blinded manner. This will help establish 1) intercurrent events for the efficacy estimands, and 2) whether a subject will be excluded from the Per Protocol Set(s). All rescue therapies identified by the medical reviewers per the algorithm below will be imported in programming. This process will be repeated until database lock and the list of all rescue therapies identified will be finalized before study unblinding.

Only medications and medical procedures reported on the electronic case report forms (eCRFs) can be assessed whether they are rescue therapy for UC. If the exposure happens in the follow-up period (beginning on or after the date of last study treatment administration), then it would not be considered as a rescue therapy. Impact of rescue therapy use in the analysis is timing-dependent, eg, if a subject starts a rescue therapy between their Week 12 and Week 52 endpoint assessments, then it may have potential impact on Week 52 endpoint analysis but will have no impact on Week 12 endpoints. The rules outlined below apply to both new use and increase in dose from Baseline.

Biologics with immunomodulatory properties

- Rule:
 - Any exposure after first dose
- List of medications:
 - AntiTNF α antibodies:
 - ADALIMUMAB
 - CERTOLIZUMAB
 - CERTOLIZUMAB PEGOL
 - GOLIMUMAB
 - INFLIXIMAB
 - Other Biologics:
 - USTEKINUMAB
 - VEDOLIZUMAB

Nonbiologics with immunomodulatory properties

- Immunosuppressants
 - Rules to consider for Week 12 efficacy endpoints:
 - After first dose and up to and including Week 8: any increase from baseline for more than 5 days
 - After Week 8: Any dose above baseline

-
- Rules to consider for Week 52 efficacy endpoints:
 - After Week 12 and up to and including Week 40: any increase from baseline for more than 5 days
 - After Week 40: Any dose above baseline
 - List of medications:
 - MERCAPTOPYRINE
 - AZATHIOPRINE
 - TIOGUANINE
 - METHOTREXATE
 - METHOTREXATE SODIUM
 - 5-ASA COMPOUNDS
 - Rules to consider for Week 12 efficacy endpoints:
 - After first dose and up to and including Week 8: any increase from baseline for more than 5 days
 - After Week 8: Any dose above baseline
 - Rules to consider for Week 52 efficacy endpoints:
 - After Week 12 and up to and including Week 40: any increase from baseline for more than 5 days

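### Appendix 7 stops counting rescue at the last study dose, while Table 1 and Section 16.1.2 run it to the endpoint assessment; the passages need to be reconciled

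*SAP*

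**What the plan says.** Four places in the SAP bear on this.

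- **Section 2.5, Table 1.** Subjects with rescue medication, a UC dose increase or a rescue procedure "before the efficacy assessment will be treated as nonresponders". The anchor is the assessment. The footnote sends the reader to Appendix 7 for what counts as rescue.
- **Section 16.1.2.** If an efficacy measurement follows the start or increase of a UC medication, "the observed data will be censored at the time of initiation or dose increase and they will be considered as having a nonresponse". There is no limit at the last dose. The same section makes discontinuation for disease worsening, inefficacy or a UC-related adverse event a known nonresponse, whatever the rescue status.
- **Appendix 7.** For exposure in the follow-up period, "beginning on or after the date of last study treatment administration), then it would not be considered as a rescue therapy". The same appendix gives biologics the rule "Any exposure after first dose", and says that the impact of rescue depends on its timing, with an example set by endpoint assessments.
- **Section 6.4 and Table 2.** Apart from the follow-up visits, "data from all visits including scheduled, unscheduled, and ET visits will be eligible for allocation to an analysis visit". The endoscopy windows are Days 66 to 113 for Week 12 and Days 337 to 393 for Week 52, extended to Days 141 and 421 for COVID-19-impacted assessments.

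Protocol Section 5.1 places the Early Termination (ET) visit up to 7 days after the last dose and ahead of any new therapy. It also allows for late ET visits: at 2 weeks or more after the last dose, "the 2-Week Follow-Up visit is not required; however, the 4-Week Follow-Up visit should be scheduled and completed". Table 8 footnote b covers a Week 52 visit 4 weeks or more after the last dose. Section 9.6 lets the parts of a visit be split: "These may take place on different days within the study visit window".

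**The concern.** An endoscopy that feeds a co-primary endpoint can come after the last study dose. In the interval between the two, Table 1's timing and Section 16.1.2 make new UC therapy a nonresponse, while Appendix 7 says it is not rescue. Appendix 7 governs in practice, because the blinded reviewers classify by it and their list is imported into programming. Followed as written, it would keep the observed endoscopic and symptom scores, and a subject in remission on them would be a responder.

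The supporting analyses would not reliably show this. The Per Protocol Sets (Section 5.4) take their rescue criterion from the same appendix, so only the general review of protocol deviations might catch such a subject. The sensitivity analyses in Section 16.1.4 act on missing scores, and here the scores are observed. Section 3.3, which lists changes from the protocol, does not mention the last-dose cut-off, although Protocol Section 10.4 contains none: it assigns nonresponse from the start of a disallowed agent onward, or handling by Per Protocol analysis.

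**Working it through.** **1. The plan's own figure.** The point rests on no stated number. The planned power is used below only for scale. With 280 and 140 subjects and Fisher's exact test at one-sided 0.025, exact enumeration gives 92.8% for 23.5% against 10.0% at Week 52 (stated 93.4%), and 95.6% for 18.5% against 6.0% at Week 12 (stated 96%). Both agree within one point.

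**2. Is the interval reachable?** Take the last dose on the scheduled visit day and the end of the Table 2 window:

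- Week 12: 113 − 85 = 28 days; COVID-19-impacted, 141 − 85 = 56 days.
- Week 52: 393 − 365 = 28 days; COVID-19-impacted, 421 − 365 = 56 days.

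An endoscopy that many days after the last dose is still accepted, and more if dosing stopped before the scheduled day.

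**3. One hypothetical subject under each rule.** Last dose on Day 340 for a reason unrelated to UC, a biologic started on Day 343, ET endoscopy on Day 346.

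- The endoscopy is 346 − 340 = 6 days after the last dose, inside the 7-day ET limit, and Day 346 lies in 337 to 393, so it is a Week 52 value.
- Table 1 timing: Day 343 precedes Day 346, so nonresponder.
- Section 16.1.2: data censored from Day 343, so nonresponder.
- Appendix 7 biologics rule alone: exposure after the first dose, so rescue.
- Appendix 7 follow-up sentence: Day 343 is after Day 340, so not rescue, and the subject can count as a remitter.

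The example shows conflicting classification. It does not suggest that three days of a biologic would produce remission; a longer gap leaves more room for that.

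**4. Who remains after the plan's safeguards.** Subjects who stop for UC-related reasons drop out, because Section 16.1.2 already makes them nonresponders. Two groups are left: those who stop for other reasons and start UC therapy before an in-window endoscopy, and completers with a gap between the last dose and the Week 52 endoscopy. The first group requires a departure from the instruction to hold the ET visit before new therapy. No such sentence is attached to a completer's Week 52 visit.

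**5. Weight of one subject.** 1/280 = 0.36 percentage points on etrasimod; 1/140 = 0.71 on placebo. These denominators are planned enrolment. The primary set is the FAS with Baseline MMS 5 to 9, so if it is no larger than planned enrolment, each case weighs at least this much.

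**6. Illustration of scale.** The documents give no count of affected subjects, so the counts here are assumed. If 1, 2, 3 or 5 of the expected etrasimod responders at Week 52 became nonresponders and placebo did not change, the etrasimod rate would be 23.1%, 22.8%, 22.4% or 21.7%, and power 91.5%, 90.1%, 88.6% or 85.0%. If the same totals were split 2:1 across the arms, both rates would fall by the same amount and power would not drop (93.1%, 93.4%, 93.7%, 94.3%).

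**The case against.** The best reply is that there is no contradiction: Appendix 7 defines rescue, Table 1 adds timing, and the Appendix 7 sentence is about the follow-up period. Protocol Section 10.4 also speaks of agents disallowed in combination with study treatment, which gives an on-treatment definition some basis. This does not remove the conflict. The parenthesis fixes the follow-up period by the last dose and not by the endpoint. On that reading Table 1's timing words have no effect in the interval, and Section 16.1.2 and the biologics rule stay contradicted.

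The arguments about reach largely stand:

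- The subjects most likely to need new UC therapy are already nonresponders.
- The protocol's text on gaps of 2 and 4 weeks says when follow-up visits may be skipped. A reader might infer that late endoscopies are planned; the text does not say so.
- Other UC treatments are prohibited during the study. On visit days the dose is taken at the site after the pre-dose assessments, and subjects waiting to enter the extension may receive bridging supply. A completer's last dose and Week 52 visit therefore normally lie close together.
- A reader might infer that both co-primary endpoints are equally exposed. They are not: anyone who continues past Week 12 has a last dose after that assessment. Table 8 also waives endoscopy for discontinuation at or before Week 16, and an ET endoscopy between the two windows feeds neither endpoint.

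A reader might also infer a bias in favour of etrasimod. The documents do not support that. The rule is the same in both arms, and a retained placebo remission would work against etrasimod.

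**Conclusion.** The inconsistency is real and affects the derivation of both co-primary endpoints, mainly Week 52. Two programmers, one following Table 1 and Section 16.1.2 and the other Appendix 7, could give the same subject different outcomes.

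The practical effect is probably small. Neither its size nor its direction can be derived from the documents. The minimum weights of 0.36 and 0.71 points per subject rest on the assumption that the primary set does not exceed 280 and 140; they are not estimates of bias. The power illustration rests on assumed counts and on all affected responders being in one arm. Nothing here supports a claim that the trial's conclusion is at risk. The case for acting is that the rule is ambiguous, the correction is cheap, and the rescue list has to be final before unblinding.

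**What to change.** Reconcile Table 1, Section 16.1.2 and Appendix 7 by changing only the timing anchor of the Appendix 7 exclusion. Possible wording: *Exposure beginning after the assessment used for an endpoint is not rescue for that endpoint; exposure beginning before that assessment is classified by the drug-class rules below, whether or not study treatment has stopped.*

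The last clause matters. Declaring every exposure before the assessment to be rescue would override Appendix 7's own thresholds (more than 5 or 7 days, or more than one parenteral dose, depending on class and period), and those should stay as they are. The text should also say which date counts as the assessment (for clinical remission, the endoscopy date) and how a start on that same day is handled.

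The cost is one or two sentences and a repeat of the blinded classification for UC exposures that began on or after the last dose, before the rescue list is finalised and the study unblinded. Reporting the number of such exposures by arm would show whether the point mattered. The change concerns analysis classification only and has no bearing on how subjects are treated.
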